# **Secondary Objectives:**

To demonstrate non-inferiority of Insulclock compared with standard insulin pen device on:

[figure not shown]
- Treatment satisfaction -Diabetes Treatment Satisfaction Questionnaire Status (DTSQs)
- Diabetes Related Quality of Life (DRQoL)
- Adherence:
  - Frequency of insulin irregularities (omission, mistiming and dosing)
- Glycemic control:
  - Glycemic control, as measure by change in mean HbA1c from baseline
  - Frequency of hypoglycemia
  - o 7-point SMBG profile
  - Daily fasting glucose profile

# Methods:

This will be a randomized (1:1), controlled, 26-week cross-over clinical trial in patients with inadequately controlled T2D (HbA1c  $\geq$  7.0% to  $\leq$  12.0%) while treated with oral antidiabetic agents and basal insulin (NPH, glargine or detemir). Participants will be randomized to use the Insulclock device (Group 1) and standard of care using an insulin pen device (Group 2). All patients will use the Insulclock device attached to glargine U100 insulin pens (SoloStar®) during the study period. During the study period. Participants in Group 1 will receive daily information on their smartphone on insulin administration (time and dosing) as well as reminders in the event of missing doses. Participants in Group 2, will use the Insulclock, but will not receive feedback on insulin treatment or alerts.

Randomization will be stratified by:

• HbA1c at Screening (<8.0%, >8.0%)

### **Study Visits**

Screening (Visit 1)

Approximately 1-2 weeks prior to the start of the study, all potential study patients will be screened to check their eligibility after signing the informed consent form (ICF) and assigned a patient identification number. Medical history, physical examination, height, weight, vital signs, pre-existing conditions, and concomitant medications will be recorded during this visit. Laboratory assessments performed at Visit 1 to determine eligibility for the study include pregnancy tests for females, and HbA1c, serum chemistry, assays. Patients who do not meet all the inclusion criteria at Visit 1 will be considered screen failures and will not be randomized to participate in the study.

Eligible patients will be trained on the use of the glucometer to monitor their BG levels. Patients will be given diabetes diaries and associated training to record all glucose levels, insulin doses, and episodes of hypoglycemia.

Insulin administration technique will be reviewed prior to randomization to ensure good technique. Reinforcement will be provided as needed during the follow-up visits.

Only eligible patients treated with a once daily insulin dose of NPH, detemir, glargine insulin will be switched to SoloSTAR pen (glargine U100) at a total dose (TDD).

Antidiabetic agents will be continued at the same dose, except insulin secretagogues which can be stopped if HbA1c is <8% or reduced by half if HbA1c is >8%.

Patients will be instructed in performing glucose testing at home before meals, with a minimum of 2 out of the 4 pre-meal and bedtime glucose measurements per day. In addition, patients must perform a 7-point SMBG (fasting, before meals, 2 hours after meals, and bedtime) done between 3 to 5 days prior to Visit 2.

One week after screening and before randomization, eligible participants will receive an Insulclock device. They will be properly trained on how to use it, charge and connect Insulclock to their mobile devices. Insulcloud will make smartphone available for subjects, who do not own a smartphone, during the course of the study. Technique skills such as the ability to navigate the app, press the button for 5 seconds while giving insulin injection, and how to connect the device to their phones will be explained. They will be asked to use the Insulclock with their insulin pen, to get familiarized with it. An assessment will be done after the week of using the device in order to review quality and understanding of the technology. Those subjects that fail to use the device properly will be deemed Screen Failures.

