# Instructions to be provided to Patients in Preparation for Visit 2 (Randomization visit)

- All patients will be instructed to provide daily glucose records. In addition, they will perform a 7-point SMBG done between 3 to 5 days prior to Visit 2.
- Insulclock usage, compliance, and technique will be reviewed.
- Patients who complied with the 7-point glucose testing (fasting, before meals, 2 hours after meals, and bedtime) and fulfill the eligibility criteria at Visit 2 will be randomized to participate in the study.
- Diabetes Treatment Satisfaction Questionnaire Status (DTSQs)

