# Visit 14 (End of Study)

- Diabetes Treatment Satisfaction Questionnaire Status (DTSQs)
- Blood sampling for HbA1c assessment to determine efficacy of treatment
- Study diaries collected and reviewed for BG levels, episodes of hypoglycemia, insulin self-administration

During each visit, participants will have their insulin dose titrated to achieve a fasting glucose <130 mg/dL as detailed in the glargine titration algorithm. Once the fasting glucose 3-day average is <130 mg/dL, insulin doses will be kept constant, unless the participant experiences recurrent hypoglycemia or severe hyperglycemia.

**Insulin Glargine Titration Schedule.** Make adjustment every 3 days after the subject has been on insulin U100 as follows:

Mean 3 day consecutive Fasting SMBG	Glargine U100 Dose Adjustment	
>180 mg/dL	Increase glargine dose by 4 IU	
$130 - \le 180 \text{ mg/dL}$	Increase glargine dose by 2 IU	
$71 - \le 130 \text{ mg/dL}$	No change	
$\leq 70 \text{ mg/dL}$	Decrease insulin glargine dose by 10%	
$\leq$ 40 mg/dL	Decrease insulin glargine dose by 20-30%	

Upward titration should be stopped for one week after a case of hypoglycemia confirmed by a SMBG reading < 70 mg/dL unless there is an adequate explanation (e.g. omission of a meal) for the event. The study staff should instruct the subject to contact the site for any questions on the insulin dose adjustments.

Treatment satisfaction will be assessed with the Diabetes Treatment Satisfaction Questionnaire Status (DTSQs)  to be administered at baseline (week 0) and at weeks 12 and 24 to assess relative changes in the DTSQ between interventions. The amplitude of the score on the DTSQc gives the degree of change in satisfaction while the direction (positive or negative) will provide guidance on the preference of one device over the other.

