# **Assessment of Results:**

The primary outcome of *treatment adherence* with the use of Insulclock with feedback or no feedback information (blinded) will be determined by the percentage of patients and number of insulin omission, mistiming and dosing. Number insulin irregularities will be registered on the Insulclock device and data will be retrieved during each clinic visit.

**For treatment satisfaction**, subjects' responses to questions 1, 7 and 8 of the DTSQc will be used. A comparison of the score on the DTSQs from week 12 to week 24 as well as using the score on the other questions of the DTSQc, which would overcome the ceiling limitation of using the DTSQs by itself, will also be used to assess treatment satisfaction . The Diabetes Treatment Satisfaction Questionnaire Status (DTSQs) form will be administered at weeks 0, 12 and 24.

Questionnaires will be given at week 0 for standardization purposes. The amplitude of the score on the DTSQc gives the degree of change in satisfaction while the direction (positive or negative) will provide guidance on the preference of one device over the other (i.e., if we predict that patients greatly prefer alarm reminders over nothing and he/she started the group 1 with daily reminders then transitioned to group 2 without the daily reminders, his/her score would be '-3', whereas if he/she was initially not getting the daily reminders followed by the daily reminders then the score would be '+3').

**Ouality of life** will be assessed at baseline and again at weeks 12 and 24 in order to determine the impact of the type of therapy on this outcome. Patients will be given the Diabetes Quality of Life Clinical Trial Questionnaire-Revised (DQLCTQ-R), the Problem Areas In Diabetes scale (PAID) and the Elderly Diabetes Burden Scale (EDBS) at baseline, weeks 12 and 24 to assess their quality of life and any potential impact of the treatment regimen .

*Glycemic Control* will be assessed via HbA1c at weeks -1, 12 and 24 and via fasting blood glucose averages at weeks 0, 12 and 24 from point of care testing during the preceding week.

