# **Statistical Analysis:**

This pilot study will compare treatment irregularities (insulin omission, mistiming and dosing) between Insulclock versus conventional insulin injection pen device. We will also compare differences in glycemic control, as measured by change in mean HbA1c from baseline, number of hypoglycemic events, percentage of subjects maintaining therapy, 7-point SMBG profile, fasting plasma (FPG) profile, and HRQoL assessments (Patient reported outcomes) between groups.

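### The home-testing minimum can be met without any fasting reading, although titration and the fasting outcomes depend on one; and the 7-point profile compared between groups is scheduled only before randomization

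*Combined protocol and SAP*

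**What the plan says.** **Home testing.** The instructions for Screening (Visit 1), Randomization (Visit 2) and the Interim Visits (5 and 11) all tell patients to test before meals, "with a minimum of 2 out of the 4 pre-meal and bedtime glucose measurements per day". None of the three names a reading that must be included.

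**Titration.** The schedule printed under Visit 14 (End of Study) opens with "Make adjustment every 3 days after the subject has been on insulin U100 as follows", and every row is entered with "Mean 3 day consecutive Fasting SMBG". The hold rule in the same section uses the same quantity: "Once the fasting glucose 3-day average is <130 mg/dL, insulin doses will be kept constant".

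**Fasting outcomes.** Secondary Objectives lists "Daily fasting glucose profile". Assessment of Results measures glycemic control partly "via fasting blood glucose averages at weeks 0, 12 and 24 from point of care testing during the preceding week". The opening paragraph of Statistical Analysis names "7-point SMBG profile, fasting plasma (FPG) profile" among the comparisons between groups.

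**7-point profile.** It is requested at Screening and again in the preparation for Visit 2, where "they will perform a 7-point SMBG done between 3 to 5 days prior to Visit 2". The lists for Visits 5 and 11, Visit 8 and Visit 14 do not mention it.

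**The concern.** A testing minimum defines compliance. This one does not secure the only input that the titration table and the hold rule accept, nor the input to the fasting outcomes. The documents do not say what a site should do when the three fasting values are absent, and they give no rule for missing fasting readings at analysis. Glargine is titrated under both conditions, and HbA1c and hypoglycemia are outcomes. Titration that stalls, or that goes ahead on unspecified judgement, would add uncontrolled variation to the glycemic comparison. Fasting values that were never recorded cannot be recovered later.

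The 7-point gap is a separate scheduling matter and needs no assumption about patient behaviour. An outcome measured only before randomization carries no information on feedback versus no feedback.

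**Working it through.** The plan gives no figure for completeness of fasting readings, so there is none to reproduce.

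**Step 1: what the minimum allows.** Inputs: four daily readings (before each of three meals, and bedtime), of which at least two are required. The pre-breakfast reading is taken as the fasting one.

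- Exactly two readings: C(4,2) = 6 pairs. Pairs without fasting: C(3,2) = 3. Share: 3/6 = 50%.
- Exactly three readings: C(4,3) = 4 sets. Sets without fasting: C(3,3) = 1. Share: 1/4 = 25%.
- All four readings: fasting is always included.

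Pre-dinner plus bedtime every day is thus full compliance with no fasting value. These are counts of permitted patterns. They are not estimates of how patients behave.

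**Step 2: what this could mean for completeness.** Let q be the daily probability that a fasting reading is taken, independent across days. The documents do not give q, so every row is an assumption. q = 0.5 corresponds to choosing a pair at random each day.

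- 3-day window complete: q³
- No fasting value in 7 days: (1 − q)⁷
- Expected fasting values in 7 days: 7q
- No run of three consecutive fasting days within 7: enumeration of all 2⁷ = 128 patterns

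| q | 3-day window complete | No run of 3 in 7 days | No value in 7 days | Expected values in 7 days |
|---|---|---|---|---|
| 0 | 0% | 100% | 100% | 0 |
| 0.25 | 1.6% | 93.8% | 13.3% | 1.75 |
| 0.5 | 12.5% | 63.3% | 0.8% | 3.5 |
| 0.75 | 42.2% | 20.1% | <0.01% | 5.25 |
| 0.9 | 72.9% | 3.3% | <0.01% | 6.3 |
| 1 | 100% | 0% | 0% | 7 |

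The titration input is far more sensitive than the weekly average. At q = 0.9, 100% − 72.9% = 27.1% of 3-day windows are incomplete, while a 7-day average still rests on about 6 values. A wholly empty weekly average is a concern mainly for patients who rarely or never take the fasting reading.

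**Step 3: other sources of fasting values.** The 7-point test is the only scheduled test that names a fasting reading. It falls three to five days before Visit 2, and randomization requires that it was done, so the week 0 average has at least one value. No such test precedes Visits 8 or 14, and none of the visit lists includes a fasting plasma draw. Weeks 12 and 24 therefore depend on the home readings.

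**Step 4: the 7-point profile.** Compared between groups: yes (Secondary Objectives; Statistical Analysis). Scheduled before randomization: yes. Scheduled after randomization: nowhere. On-treatment profiles per patient if the plan is followed exactly: 0.

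**The case against.** The best reply is that the passages can be read together. The leading instruction is to test before meals, which includes breakfast; two of four is only a floor; and a daily fasting outcome plus a 3-day fasting mean imply that fasting readings are expected. On that view the defect is an unstated link and not an outright contradiction. This is fair, but the link is the part that patients and sites need in writing, and the floor is the only stated standard.

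Several stronger readings are tempting, and the documents do not support them:

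- *A reader might take 12.5% as the expected completeness.* It rests on random choice of pairs, which is doubtful for people whose basal insulin is titrated on fasting values.
- *A reader might infer that patients will go 24 weeks without a fasting value.* The minimum permits it, but telephone contact every two weeks and diary review at clinic visits make it unlikely to go unnoticed.
- *A reader might infer bias between feedback and no feedback.* Patients know which condition they are in, so differential recording is possible. However, the feedback concerns injections and not glucose testing, and in a crossover a stable testing habit is largely shared by both conditions. Bias is not shown.
- *A reader might infer that every dose decision rests on fasting values.* The pause in upward titration after a confirmed reading below 70 mg/dL is not limited to fasting readings, and Protection against Risks links dose reduction to hypoglycemia in general.

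The plasma profile in Statistical Analysis might mean a laboratory measure, but no draw for it is scheduled. The scope is also limited: the primary outcome is recorded by the device, and Analysis of Secondary Endpoints names neither fasting glucose nor the 7-point profile. Both are nonetheless stated as outcomes elsewhere in the plan. None of these replies touches the 7-point scheduling gap.

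**Conclusion.** The point holds as a mismatch between what must be measured and what the plan then uses. Half of the minimal testing patterns (3 of 6) supply no fasting value, so compliant patients can lack the titration input and the week 12 and 24 fasting averages. The documents establish that this can happen and not how often: across the assumed range of q, the complete share of 3-day windows runs from 0% to 100%. The 7-point finding is firmer. As scheduled, the planned comparison between conditions cannot be made. Both matters affect secondary glycemic outcomes in a pilot study. They should be corrected, but they do not threaten the primary analysis.

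**What to change.** 1. The sponsor should reconcile the testing minimum (Visit 1, Visit 2 and Interim Visits) with the fasting inputs already required under Secondary Objectives, Assessment of Results and the titration schedule, so that the required readings supply them. How to do so is for the sponsor to decide; no dose, titration or monitoring rule is proposed here. Cost: wording in three visit lists and the diary instructions.
2. Either add the existing 7-point profile to the preparation for Visits 8 and 14, or remove it from the between-group outcomes in Secondary Objectives and Statistical Analysis. Cost: two further diary days per patient if it is kept, and a text edit if it is dropped.

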# Instructions to be provided to Patients in Preparation for Visit 2 (Randomization visit)

- All patients will be instructed to provide daily glucose records. In addition, they will perform a 7-point SMBG done between 3 to 5 days prior to Visit 2.
- Insulclock usage, compliance, and technique will be reviewed.
- Patients who complied with the 7-point glucose testing (fasting, before meals, 2 hours after meals, and bedtime) and fulfill the eligibility criteria at Visit 2 will be randomized to participate in the study.
- Diabetes Treatment Satisfaction Questionnaire Status (DTSQs)

# **Randomization (Visit 2)**

- Patients will receive detailed instruction on the use of Insulclock system according to randomization group.
- Study diaries will be collected and reviewed for BG levels, episodes of hypoglycemia, insulin selfadministration
- Dose of glargine insulin will be adjusted as needed (page 8).

• Patients will be instructed in performing glucose testing at home before meals, with a minimum of 2 out of the 4 pre-meal and bedtime glucose measurements per day.

# Telephone Visits (visit 3, 4, 6, 7, 9, 10, 12, 13)

• Between each office visit, patients will have a telephone visit with the investigator at 2 week intervals after randomization (Visit 2) and interim office visits (visits 5 and 11).

# Interim Visits (visit 5 and 11)

The following activities occur during interim visits:

- Patients will receive detailed instruction on the use of the Insulclock system
- Study diaries will be collected and reviewed for BG levels, episodes of hypoglycemia, insulin selfadministration
- Dose of glargine insulin will be adjusted as needed (page 8).
- Patients will be instructed in performing glucose testing at home before meals, with a minimum of 2 out of the 4 pre-meal and bedtime glucose measurements per day.

# Crossover visit (Visit 8, week 14)

The following activities occur during crossover visit:

- At midpoint (week 12), patients will be converted to the alternate treatment Arm (cross-over design).
- Patients will receive detailed instruction on the use of the Insulclock system
- Diabetes Treatment Satisfaction Questionnaire Status (DTSQs)
- Blood sampling for HbA1c assessment to determine efficacy of treatment
- Study diaries collected and reviewed for BG levels, episodes of hypoglycemia, insulin self-administration
- Dose of glargine insulin will be adjusted as needed (page 8).

# Visit 14 (End of Study)

- Diabetes Treatment Satisfaction Questionnaire Status (DTSQs)
- Blood sampling for HbA1c assessment to determine efficacy of treatment
- Study diaries collected and reviewed for BG levels, episodes of hypoglycemia, insulin self-administration

During each visit, participants will have their insulin dose titrated to achieve a fasting glucose <130 mg/dL as detailed in the glargine titration algorithm. Once the fasting glucose 3-day average is <130 mg/dL, insulin doses will be kept constant, unless the participant experiences recurrent hypoglycemia or severe hyperglycemia.

**Insulin Glargine Titration Schedule.** Make adjustment every 3 days after the subject has been on insulin U100 as follows:

Mean 3 day consecutive Fasting SMBG	Glargine U100 Dose Adjustment	
>180 mg/dL	Increase glargine dose by 4 IU	
$130 - \le 180 \text{ mg/dL}$	Increase glargine dose by 2 IU	
$71 - \le 130 \text{ mg/dL}$	No change	
$\leq 70 \text{ mg/dL}$	Decrease insulin glargine dose by 10%	
$\leq$ 40 mg/dL	Decrease insulin glargine dose by 20-30%	

Upward titration should be stopped for one week after a case of hypoglycemia confirmed by a SMBG reading < 70 mg/dL unless there is an adequate explanation (e.g. omission of a meal) for the event. The study staff should instruct the subject to contact the site for any questions on the insulin dose adjustments.

Treatment satisfaction will be assessed with the Diabetes Treatment Satisfaction Questionnaire Status (DTSQs)  to be administered at baseline (week 0) and at weeks 12 and 24 to assess relative changes in the DTSQ between interventions. The amplitude of the score on the DTSQc gives the degree of change in satisfaction while the direction (positive or negative) will provide guidance on the preference of one device over the other.

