# Potential Risks to the Subjects:

There are no major risks associated with the intervention.

**Hypoglycemia.** It is possible that following the proposed protocol, patients receiving basal glargine and metformin may develop hypoglycemia. For this analysis, **symptomatic hypoglycemia** is defined as an event with typical symptoms (i.e., sweating, palpitation, and feeling of hunger) with or without confirmation by plasma glucose <54 mg/dl (3.9 mmol/L).

Severe hypoglycemia is defined as episodes necessitating assistance and associated with measured plasma glucose < 40 mg/dl (2.2 mmol/L) or with prompt recovery after administration of carbohydrates, glucagon, or other resuscitative actions.

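### The titration schedule and the risk-protection section can give opposite dose directions after hypoglycemia

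*Combined protocol and SAP*

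**What the plan says.** Three places in the combined protocol and SAP bear on this.

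- **Insulin Glargine Titration Schedule (under Visit 14, End of Study).** The table is driven by one quantity, "Mean 3 day consecutive Fasting SMBG". Its top row reads "Increase glargine dose by 4 IU" for a mean above 180 mg/dL; means above 130 up to 180 give +2 IU. The decrease rows start at a mean of 70 mg/dL or less ("Decrease insulin glargine dose by 10" per cent), with a larger cut at 40 or less. The text after the table adds a pause: "Upward titration should be stopped for one week after a case of hypoglycemia confirmed by a SMBG reading < 70 mg/dL", which does not apply "unless there is an adequate explanation (e.g. omission of a meal) for the event". Before the table, doses are held constant once the 3-day fasting average is below 130 mg/dL, "unless the participant experiences recurrent hypoglycemia or severe hyperglycemia"; no action is stated for that exception.
- **Potential Risks to the Subjects.** An episode needing assistance is severe if it comes with a measured plasma glucose below 40 mg/dL, "or with prompt recovery after administration of carbohydrates, glucagon, or other resuscitative actions". The second branch needs no glucose value.
- **Protection against Risks.** When a patient develops hypoglycemia, the insulin dose is to be lowered, with a pointer to the treatment algorithm. The sentence has no confirmation condition, no severity limit and no exception for explained events.

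**The concern.** Protection against Risks promises a reduction and relies on the algorithm to deliver it, but the algorithm has no reduction that an event can set off. Staff who follow the pointer reach a table of 3-day fasting means and a pause that depends on a meter reading and can be waived. For the same patient on the same day, one section can call for a lower dose and another for a higher one. The events most exposed are those that the protocol itself classes as severe without a reading, because they cannot meet the pause condition, and those with a reading that are attributed to something such as a missed meal, because the waiver has no severity limit.

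Hypoglycemia is the one specific harm named under Potential Risks to the Subjects, and participants in both groups are titrated. Insulin dose and rate of hypoglycemia are also secondary endpoints, so inconsistent handling would feed into reported results as well as patient safety.

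**Working it through.** The plan states no figure on this point, so there is nothing to reproduce. The check sets the rules side by side and runs the table on readings that are **assumed for illustration**.

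**Case A: severe event, no meter reading.** Assume a daytime episode needing assistance, promptly reversed with glucagon and not metered, with fasting readings of 190, 185 and 190 mg/dL.

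1. Potential Risks to the Subjects: assistance plus prompt recovery, so the event is severe.
2. Protection against Risks: the patient has developed hypoglycemia, so the dose is lowered.
3. Pause rule: there is no SMBG reading below 70 mg/dL, so the pause condition is not met.
4. Table: (190 + 185 + 190)/3 = 565/3 = 188.3 mg/dL, above 180, so +4 IU.

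Steps 2 and 4 point in opposite directions. With assumed readings of 150, 155 and 160 the mean is 465/3 = 155.0, and the table gives +2 IU. The event itself enters neither result.

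**Case B: event with a low fasting reading.** Assume fasting readings of 39, 180 and 180 mg/dL.

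1. Table: (39 + 180 + 180)/3 = 399/3 = 133.0 mg/dL, so +2 IU.
2. Pause rule: 39 is below 70, so upward titration stops for a week, unless the event is judged adequately explained. If it is, the +2 IU row stands.
3. Protection against Risks: the dose is lowered, explained or not.

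**How high the other readings must be.** With one fasting value of 39, the other two must average:

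| Table result | Condition on the mean of three | Average of the other two |
|---|---|---|
| +4 IU | above 180 | above (540 − 39)/2 = 250.5 |
| +2 IU | above 130, up to 180 | above (390 − 39)/2 = 175.5 |
| decrease | 70 or less | at or below (210 − 39)/2 = 85.5 |

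Between the last two rows the table makes no change. For example, 39, 120 and 140 give 299/3 = 99.7. That is still not the reduction that Protection against Risks states.

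**Result.** The two sections agree on a reduction only when the 3-day fasting mean is itself 70 mg/dL or less. In the no-change row they differ. In the two increase rows they are opposed unless the pause applies, and a pause is still not a reduction.

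**The case against.** The strongest reply is that the plan does respond to hypoglycemia. Protection against Risks lowers the dose without asking for a reading or allowing an excuse. Patients are told to call the diabetes center or their primary care physician, response is monitored by telephone every 2 weeks and at clinic visits, and at the interim and crossover visits diaries are reviewed for hypoglycemia and the dose adjusted as needed. This stands. A reader who looks only at the titration text might infer that a severe event can set off nothing at all; the documents do not support that. The reply does not remove the conflict, because the reduction is stated by reference to an algorithm that does not contain it.

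Other points on that side also hold:

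- The hypoglycemia definitions are introduced as being for analysis, and a dosing rule may use a different threshold without error. The finding does not rest on the thresholds differing; it rests on two dosing statements that disagree. The severe definition only shows which events are exposed.
- The clause on recurrent hypoglycemia is not evidence of harm. It concerns holding a dose constant once the fasting average is below 130 mg/dL; a single event that fails to meet it leaves the dose unchanged, not raised.
- The absence of a planned interim analysis concerns the trial data, not the handling of one patient.
- A reader might infer several increases within the week a pause would have covered, since the schedule adjusts every 3 days. The same section also ties titration to visits, and telephone visits are 2 weeks apart, so the number of increases cannot be derived.
- The readings are constructed. They show that the rules can conflict, not how often they will.

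**Conclusion.** Wrong as written. Protection against Risks states a reduction after any hypoglycemia, while the schedule it cites has no event-based reduction and can order +2 or +4 IU after the same event, including one that the protocol classes as severe. This follows from the wording alone. The size in a given patient depends on assumed fasting means: +2 IU for means above 130 up to 180 mg/dL, +4 IU above 180, against a reduction of unstated amount in the other section. The conclusion assumes that the treatment algorithm referred to is the Insulin Glargine Titration Schedule, the only dosing algorithm in the document. The documents give no rate of unmetered or explained severe events, so the number of patients affected cannot be estimated. Nothing here says which of the two directions is clinically right.

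**What to change.** The sponsor must reconcile the Insulin Glargine Titration Schedule, Potential Risks to the Subjects and Protection against Risks so that they give one consistent direction after hypoglycemia. The revised text should:

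- cover events that count as severe without a meter reading;
- state whether the waiver for explained events applies to severe ones;
- make the cross-reference in Protection against Risks lead to a rule that the schedule actually contains.

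Which action follows an event is for the sponsor to decide. The cost is a short protocol clarification applied by existing staff.
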